## 5.3 Monitoring after Sodium Thiosulfate infusion

Because of potential hemodynamic instability following STS infusion, participants will be monitored for 30 minutes to 1 hour following completion of STS infusion. If participants manifest symptoms of hypotension (dizziness or orthostasis), IV hydration needs to be initiated following BP measurement, following the current standard of care.

## 5.4 Stopping Rules

We will use Bayesian decision rules for the study to decide respectively early stop out of safety or feasibility concerns. We expect that at least 75% of patients would receive target cumulative cisplatin dose of 200 mg/m^2 which is similar for both weekly and high dose cisplatin groups[15]. We assume that no more than 25% of patients would fail to receive cumulative cisplatin dose of 200 mg/m^2 in either cisplatin dose stratum. With the Beta prior distribution with parameters 2 and 6, the prior expected rate is set at the targeted rate of 25%, and the prior probability of the risk greater than 25% is 45%. We apply this prior distribution to the observed number of patients experiencing high grade toxicity and compute the posterior (updated) probability of the risk of such toxicities greater than 25%. In each cisplatin dose stratum we will consider stopping treatment any time if the posterior probability is at least .70(Table 1).

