**Table 5.1      Regimen Description**

Investigational Product	Premedication; precautions	Dose	Route	Schedule	Cycle Length
Cisplatin (weekly)	
 
Cisplatin can be given within 24 hours of radiation therapy. If radiation is held for more than 2 days (for any reason), cisplatin may be held as well until radiation resumes.
 
Prophylactic anti-emetic regimen will be given as per UCSF guidelines.
 
1 liter of isotonic fluid will be given intravenously prior to cisplatin infusion
 
	40 mg/m 	Intravenously	Days 1, 8, 15, 22, 29, 36, and 43	
Cisplatin (every-3-weeks)	
 
Cisplatin can be given within 24 hours of radiation therapy. If radiation is held for more than 2 days (for any reason), cisplatin may be held as well until radiation resumes.
 
Prophylactic anti-emetic regimen will be given as per UCSF guidelines.
 
1 liter of isotonic fluid will be given intravenously prior to cisplatin infusion
 
	80-100 mg/m 	Intravenously	Days 1, 22, and 43	Weekly or every 3 weeks
*Sodium Thiosulfate (weekly)	No contraindications	10 g/m 	Intravenously using a Mediport or a PICC line	Between 4-5 hours after each cisplatin infusion sodium thiosulfate will be	

				administered over 1-2 hours	
*Sodium Thiosulfate (every-3-week)	No contraindications	20 g/m 	Intravenously using a Mediport or a PICC line	Between 4-5 hours after each cisplatin infusion sodium thiosulfate will be administered over 1-2 hours	

\*Missed doses of sodium thiosulfate will not be replaced.

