**Table 1. Stopping rule for safety**

Stop, if there are this many patients who do not	2	3	4	5	6
--	---	---	---	---	---

complete cumulative cisplatin dose of 200 mg/m 					
In this many patients	2-4	5-7	8-10	11-13	14-16

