### **3. Review and Oversight Requirements**

#### **3.1 Adverse Event Monitoring**

All Grade 3-5 adverse events (AEs), whether or not considered to be expected or unexpected and whether or not considered to be associated with the use of the investigational agent(s) or study procedure, will be entered into OnCore®, UCSF's Clinical Trial Management System.

Adverse events are graded according to the Common Terminology Criteria for Adverse Events (CTCAE) as developed and revised by the Common Therapy Evaluation Program (CTEP) of the National Cancer Institute. Adverse events are further given an assignment of attribution or relationship to investigational agent or study procedure. Attribution categories are:

- **Definite** – The adverse event is clearly related to the investigational agent(s) or study procedure.
- **Probable** – The adverse event is likely related to the investigational agent(s) or study procedure.

- **Possible** – The adverse event may be related to the investigational agent(s) or study procedure.
- **Unrelated** – the adverse event is clearly not related to the investigational agent(s) or study procedure.

All Grade 3-5 adverse events entered into OnCore® will be reviewed on a monthly basis at the Site Committee meetings. The Site Committee will review and discuss the selected toxicity, the toxicity grade, and attribution assignment.

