### 3.3 Review of Adverse Event Rates

If an increase in the frequency of Grade 3 or 4 adverse events (above the rate reported in the Investigator Brochure or package insert) is noted in the study, the Principal Investigator will notify the DSMC via report at the time the increased rate is identified. The report will indicate if the incidence of adverse events observed in the study is above the range stated in the Investigator Brochure or package insert.

If at any time the Investigator voluntarily holds enrollment or stops the study due to safety issues, the DSMC Chair (or Vice Chair) and the DSMC Director must be notified within one business day and the IRB must be notified as per IRB reporting regulations.

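### Section 5.4 promises separate safety and feasibility stops but supplies one rule with two conflicting events, so it is unclear whether toxicity can trigger a stop

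*Combined protocol and SAP*

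**What the plan says.** Section 5.4 announces two kinds of early stop: "We will use Bayesian decision rules for the study to decide respectively early stop out of safety or feasibility concerns". What follows is a single rule.

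- **Target.** The 25% is introduced as a dose-delivery rate: "We assume that no more than 25% of patients would fail to receive cumulative cisplatin dose of 200 mg/m" (that is, 200 mg/m²), in either dose stratum.
- **Prior.** "With the Beta prior distribution with parameters 2 and 6, the prior expected rate is set at the targeted rate of 25" per cent, and "the prior probability of the risk greater than 25% is 45" per cent.
- **Event in the text.** The prior is then updated with the number of patients who have high-grade toxicity, and the posterior is the probability that the risk of such toxicity exceeds 25%. Stopping is to be considered, per cisplatin stratum and at any time, when that probability is at least 0.70. The sentence ends by pointing to Table 1.
- **Event in the table.** Table 1 is headed "Stopping rule for safety", but its row label counts patients who do not complete 200 mg/m² of cisplatin. Its boundaries are 2 in 2-4 patients, 3 in 5-7, 4 in 8-10, 5 in 11-13 and 6 in 14-16.

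Section 8 lists safety frequencies without a threshold. Section 8.3 plans no interim analyses and refers to section 5.3 for the stopping rules, but section 5.3 covers observation after the STS infusion. Appendix 2, section 3.1, provides that "All Grade 3-5 adverse events entered into OnCore® will be reviewed on a monthly basis at the Site Committee meetings". If grade 3 or 4 events rise above the labelled rate, Appendix 2, section 3.3, provides that "the Principal Investigator will notify the DSMC via report at the time the increased rate is identified".

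**The concern.** The abstract's hypothesis is that STS is both feasible and safe, so a reader expects a boundary for each. There is one boundary, and the text and the table disagree on what it counts.

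The two events are not interchangeable here. STS is the investigational agent and is started 4-5 hours after cisplatin. The footnote to Table 5.1 says "Missed doses of sodium thiosulfate will not be replaced", so a patient can lose STS to toxicity, continue cisplatin, and be scored in Table 1 as a completer. Completer status is also fixed before STS ends, so later STS toxicity cannot change that patient's score.

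At stake is whether the only numeric stopping boundary in the trial responds to toxicity of the agent under test. Two people who apply section 5.4 in good faith to the same data could reach opposite decisions.

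**Working it through.** **Inputs.** Beta(2, 6) prior, 25% target, 0.70 threshold and the Table 1 boundaries (section 5.4); 16 patients (section 8.1); dose days and levels (Table 5.1).

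**Formula.** With r events in n patients the posterior is Beta(2 + r, 6 + n − r). For whole-number a and b, P(p > 0.25) under Beta(a, b) equals P(X ≤ a − 1) with X ~ Binomial(a + b − 1, 0.25).

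**Step 1: reproduce the plan's figures.** Prior mean = 2/8 = 0.25. Prior P(p > 0.25) = 0.75⁷ + 7 × 0.25 × 0.75⁶ = 0.133 + 0.311 = 0.445, which matches the stated 45%. The smallest r with posterior probability at least 0.70 agrees with Table 1 at 13 of the 15 sample sizes from 2 to 16. The exceptions are n = 11 (4 events already give 0.718; the table says 5) and n = 14 (5 events already give 0.744; the table says 6). Both are one patient late, which is consistent with grouping n in threes. The arithmetic is the same for either event, so the numbers cannot show which event was meant.

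**Step 2: apply both events to the same data.** Assume that every patient in the stratum reaches 200 mg/m² and some have high-grade toxicity.

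| Stratum | Toxicity | Table 1's event | Posterior | Text's event | Posterior |
|---|---|---|---|---|---|
| 8 | 4 | 0/8 | 0.080 | 4/8 | 0.852 |
| 16 | 5 | 0/16 | 0.012 | 5/16 | 0.654 |
| 16 | 6 | 0/16 | 0.012 | 6/16 | 0.804 |

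For 0/16: Beta(2, 22) gives 0.75²³ + 23 × 0.25 × 0.75²² = 0.0013 + 0.0103 = 0.012. For 6/16: Beta(8, 16) gives P(X ≤ 7) with X ~ Binomial(23, 0.25) = 0.804. In the first and third rows the text's event meets the 0.70 trigger and Table 1's event is far from it.

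**Step 3: when completer status is fixed.** 5 × 40 = 200 mg/m² is reached on Day 29, and 2 × 100 = 200 mg/m² on Day 22. Each STS infusion follows its cisplatin dose, so the STS infusions given after 200 mg/m² is reached are those of Days 29, 36 and 43 (3 of 7) and of Days 22 and 43 (2 of 3). If Day 43 is omitted, as the study calendar allows, they are 2 of 6 and 1 of 2. At 80 mg/m² two doses give 160, so 200 mg/m² needs the third dose and only the Day 43 STS infusion follows it (1 of 3).

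**Step 4: look for another boundary.** Sections 5.3, 8, 8.3 and 8.4 and Appendix 2 contain no count or rate that triggers a stop. High-grade toxicity is given no grade, attribution or time window in section 5.4 or section 8.

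**The case against.** The strongest objection is that section 5.4 does let toxicity trigger a stop. A reader who looks only at Table 1 might infer that severe toxicity in cisplatin completers can never trigger the rule, or that the plan has no toxicity rule at all. The documents do not support that: the text applies the prior and the 0.70 threshold to high-grade toxicity, and on that reading 6 of 16 completers with toxicity meet the trigger. The statement that toxicity goes unseen holds only for Table 1 as printed.

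A second objection is that failure to reach 200 mg/m² may have been meant as the measure of toxicity. That is possible, but the plan does not say so. Section 8.4 reports high-grade toxicity as a proportion in its own right, and cisplatin can continue after STS is missed.

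A third objection is that other oversight exists. Grade 3-5 events are reviewed monthly, the DSMC reviews serious events and meets every six weeks, related deaths are reported within one business day, the investigator may hold enrolment or stop the study for safety, and section 3.5 ends treatment for unacceptable adverse events. All of this stands. It rules out the inference that a toxic regimen would run unchecked to full accrual. None of it is a numeric boundary, and none of it settles what section 5.4 counts.

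**Conclusion.** The point holds as an internal contradiction. Section 5.4 promises two stops and supplies one rule with two incompatible events. One of them, high-grade toxicity, is undefined and has no acceptable rate of its own, because the 25% is justified only as an under-delivery rate. Applied as printed, Table 1 does not respond to severe toxicity in patients who reach 200 mg/m².

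The size is the gap between 0.012 and 0.804 in the 16-patient example, or between 0.080 and 0.852 in a stratum of 8, on either side of the 0.70 trigger. These are illustrations. They assume that all patients complete cisplatin, and they use stratum sizes that the plan does not fix; they do not predict how often such data would arise. Section 5.4 says only that stopping will be considered, so a trigger is not an automatic stop.

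**What to change.** Reconcile section 5.4, Table 1 and section 8.3:

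1. State which event Table 1 counts. If it is cisplatin under-delivery, retitle the table as the feasibility rule.
2. State the separate safety rule that section 5.4 promises. It needs a defined toxicity event (grade, attribution and time window) that covers all STS doses, including those after 200 mg/m² is reached, its own acceptable rate, and its own boundary table from the Beta calculation already in section 5.4.
3. Correct the cross-reference in section 8.3 from 5.3 to 5.4.

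The sponsor sets the event definition, the acceptable rate and the action when a boundary is reached; no clinical rule is proposed here.

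The cost is a paragraph and a small table. No new visits or data are needed, because grade 3-5 events and their attribution are already recorded and reviewed monthly. The downside is that a second boundary adds some chance of a false trigger. Checked after each patient in a stratum of 8, the present boundaries trigger with probability 0.33 at a true rate of 25% and 0.06 at 10%. The figures for a safety rule would depend on the acceptable rate chosen and should be reported with it.

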## 8.3 Interim Analyses and Stopping Rules

There is no plan for interim analyses in this phase II study. Stopping rules are illustrated in section 5.3.

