## 8.4 Analyses Plans

We will report the proportion of patients experiencing high-grade toxicity with exact binomial 95% confidence intervals. We will also describe patient experiences with respect to feasibility as defined above. All other adverse events will be similarly summarized by type and grade.

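### Section 5.4 is inconsistent about the event its stopping rule counts: failure to receive 200 mg/m² of cisplatin, or an undefined high-grade toxicity

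*Combined protocol and SAP*

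**What the plan says.** Section 5.4 opens by announcing Bayesian rules for stopping early on safety or feasibility grounds. It then sets a limit: "We assume that no more than 25% of patients would fail to receive cumulative cisplatin dose of 200" mg/m², in either dose stratum. A Beta(2,6) prior is centred on this 25% rate, with a stated prior probability of 45% that the rate exceeds it.

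The next sentence says what to count. It reads "We apply this prior distribution to the observed number of patients experiencing high grade toxicity", and goes on to "compute the posterior (updated) probability of the risk of such toxicities greater than 25"%. The decision sentence follows: in each stratum, "we will consider stopping treatment any time if the posterior probability is at least .70", with a pointer to Table 1.

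Table 1 is titled "Stopping rule for safety". Its row label counts patients who do not "complete cumulative cisplatin dose of 200 mg/m"². Its boundaries are 2 events in 2-4 patients, 3 in 5-7, 4 in 8-10, 5 in 11-13 and 6 in 14-16.

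Section 8.4 uses the toxicity term as an outcome of its own: "We will report the proportion of patients experiencing high-grade toxicity with exact binomial 95% confidence intervals". Section 8.3 says "Stopping rules are illustrated in section 5.3", but Section 5.3 covers monitoring after the thiosulfate infusion; the rules are in 5.4.

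**The concern.** The limit, the prior and the table's row label all concern a dose-completion event. The sentence that carries out the update concerns a toxicity event. No toxicity comes before it in 5.4 for *such toxicities* to refer to.

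The term has no grade, attribution or time window in 5.4 or 8.4. The list of safety measures at the start of Section 8 does not contain it. Appendix 2 records Grade 3-5 events but does not call them high-grade toxicity or tie them to the stopping rule.

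The rule is applied continuously, within stratum, from the second patient. Whoever keeps the count has to decide which sentence governs, and the two readings can disagree in either direction.

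**Working it through.** **Inputs (Section 5.4 and Table 1).** Prior Beta(2,6); limit 0.25; cut 0.70; the Table 1 boundaries above.

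**Formula.** After x events in n patients the posterior is Beta(2+x, 6+n−x). The rule uses P(rate > 0.25). With whole-number parameters this equals P(Y ≤ 1+x), where Y is binomial with 7+n trials and probability 0.25.

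**The plan's own figures.** Prior mean = 2/(2+6) = 0.25, as stated. Prior P(rate > 0.25) = 0.75⁷ + 7 × 0.25 × 0.75⁶ = 0.1335 + 0.3115 = 0.445, matching the stated 45%.

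**Can the two events give opposite answers?** No event rate is assumed; these are possible counts in the first 4 patients of a stratum.

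- *Case A: toxicity without dose failure.* Two patients have high-grade toxicity and all four receive 200 mg/m². The updating sentence gives 2/4: Beta(4,8), 0.713, which crosses 0.70. Table 1 gives 0/4: Beta(2,10), 0.197. If the toxicity is grade 3-4 mucositis, which the mucositis paragraph of Section 5.2 calls expected and not normally a reason for a treatment break, this case assumes that such events count as high-grade toxicity. The protocol does not say.
- *Case B: dose failure without toxicity.* Two patients withdraw after at least one thiosulfate dose and before 200 mg/m², and nobody has high-grade toxicity. Section 3.5 allows withdrawal, and Section 3.2 replaces only patients who received no thiosulfate. Table 1 gives 2/4 = 0.713; the updating sentence gives 0/4 = 0.197. Nothing here depends on how mucositis is classed.

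At the end of the next band the contrast is 3/7 = 0.742 against 0/7 = 0.101.

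**Does Table 1 match the stated 0.70 cut?** The smallest x with posterior of at least 0.70 agrees with Table 1 at 13 of the 15 values of n from 2 to 16. The later bands are:

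| n | Posterior one event below the stop | Posterior at smallest x ≥ 0.70 | Smallest x | Table 1 |
|---|---|---|---|---|
| 10 | 0.5739 | 0.7653 | 4 | 4 |
| 11 | 0.5187 | 0.7175 | 4 | **5** |
| 12 | 0.6678 | 0.8251 | 5 | 5 |
| 13 | 0.6172 | 0.7858 | 5 | 5 |
| 14 | 0.5666 | 0.7436 | 5 | **6** |
| 15 | 0.6994 | 0.8385 | 6 | 6 |
| 16 | 0.6537 | 0.8037 | 6 | 6 |

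Table 1 asks for one event too many at n=11 and n=14. No other single cut explains this: the table stops at 2/4 (0.7133) but not at 4/11 (0.7175). These two rows come into play only if one stratum reaches 11 or 14 of the 16 patients.

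**The case against.** The strongest reply is that nobody would be misled. The decision sentence points to Table 1, and Table 1 says plainly whom to count, so a team working from the table has no ambiguity about the event. Stopping is only to be considered. Toxicity is followed separately: Appendix 2 has Grade 3-5 events reviewed monthly by the Site Committee, and an excess of Grade 3 or 4 events reported to the DSMC. All of this stands, and it keeps the severity modest. It does not make the text consistent, because the updating sentence still names another event.

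A second reply is that Cases A and B are constructed. That is so. They show that the readings can conflict, not how often they would.

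A reader might infer that the toxicity wording is simply the wrong event and that dose failure was evidently meant. The documents do not support that certainty. Section 5.4 opens with safety as well as feasibility, Table 1 carries a safety title, and 8.4 reports high-grade toxicity. These fit equally well with a toxicity rule whose specification was dropped or merged. That the prior reproduces most of Table 1 does not settle the matter either, since the same prior, limit and cut give the same boundaries for any event; only the row label ties the table to cisplatin dose.

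A reader might also infer that severe toxicity goes unwatched. The Appendix 2 reviews contradict that.

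**Conclusion.** The point holds as an internal inconsistency. The limit, the prior and the row label concern failure to receive 200 mg/m²; the updating sentence concerns an undefined toxicity; the table title says safety. The readings can differ by 0.713 against 0.197 after four patients, on opposite sides of the 0.70 cut. That result rests only on the stated prior, limit and cut and on the illustrative counts. It says nothing about how likely such counts are.

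Dose failure is the only event with a stated limit and boundary table, so it is the natural one to write in. Which event the authors intended cannot be proved from the documents, so the correction needs their confirmation. The mismatch at n=11 and n=14 is a second, smaller conflict in the same rule. Correcting the event wording alone would leave it in place.

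This should be fixed, but it is not evidence that the Bayesian design is unsound or that patients are unprotected.

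**What to change.** 1. Ask the investigators whether a toxicity stopping rule was intended. If so, give it its own event definition (grade, attribution, window), limit and boundary table.
2. In the updating sentence of 5.4, replace *experiencing high grade toxicity* with *who fail to receive cumulative cisplatin dose of 200 mg/m²*, and *such toxicities* with *such failure*.
3. Retitle Table 1 as a feasibility (dose-completion) rule. If no toxicity rule is intended, amend the opening sentence of 5.4 so that it no longer promises one.
4. Align Table 1 with the 0.70 cut: 2 events in 2-4 patients, 3 in 5-7, 4 in 8-11, 5 in 12-14 and 6 in 15-16.
5. While editing, correct the pointer in 8.3 from 5.3 to 5.4.

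**Cost.** Steps 2, 3 and 5 are wording only; the prior, the 0.70 cut, the 200 mg/m² threshold and the sample size do not change. Step 4 makes the rule slightly stricter. If all 16 patients were in one stratum and the rule were checked after each, the chance of crossing a boundary would rise from 41.6% to 44.3% at a true failure rate of 25%, from 6.5% to 6.9% at 10%, and from 81.3% to 83.4% at 40%. A separate toxicity rule, if wanted, is a design decision for the investigators.

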### 3.2 Sample Size

Target accrual is a total of 16 patients, and to account for screen failures and withdrawals, we will consent up to 18 patients. Patients can be enrolled to the and can get concurrent chemoradiation with weekly cisplatin (40 mg/m^2) given once a week or concurrent chemoradiation with high dose cisplatin (80-100 mg/m^2) given every 3 weeks. Participants who do not receive any dose of STS will not be evaluable and will be replaced.

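### Table 1's stopping boundaries are one failure too lenient at 11 and 14 patients under the Beta(2,6), posterior at least 0.70 rule in Section 5.4

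*Combined protocol and SAP*

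**What the plan says.** Section 5.4 (Stopping Rules) specifies a Bayesian monitoring rule. On the prior it says: "With the Beta prior distribution with parameters 2 and 6, the prior expected rate is set at the targeted rate of 25"%. It adds that "the prior probability of the risk greater than 25% is 45"%. After each update the quantity of interest is the posterior probability that the rate is above 25%, and the action threshold is: "In each cisplatin dose stratum we will consider stopping treatment any time if the posterior probability is at least .70(Table 1").

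Table 1 then lists the boundaries. Its first row begins "Stop, if there are this many patients who do not" and counts patients who fall short of 200 mg/m² cumulative cisplatin. Its second row, "In this many patients", gives the ranges:

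| Failures needed to stop | 2 | 3 | 4 | 5 | 6 |
|---|---|---|---|---|---|
| Patients (Table 1) | 2-4 | 5-7 | 8-10 | 11-13 | 14-16 |

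Section 3.2 puts the target accrual at 16 in total and fixes no split between weekly and every-3-week cisplatin. Section 8.3 plans no interim analyses and refers the reader to the stopping rules.

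**The concern.** The prior, reference rate, cutoff and timing are all stated, so every entry in Table 1 can be derived with no outside figure. The printed ranges advance in regular blocks of three patients, whereas posterior boundaries need not do so. A table that departs from its rule gives two answers to one question: at some counts the text says the criterion is met and the table says carry on.

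This is the trial's only quantitative stopping rule, and it protects patients on definitive chemoradiation from continuing if too many fail to reach the target cisplatin dose. If text and table conflict, whoever monitors the trial must choose between them after seeing the data. Prespecification is meant to prevent that.

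**Working it through.** **Inputs.** Prior Beta(2,6), reference rate 0.25 and cutoff 0.70 (Section 5.4); boundary counts and ranges (Table 1); total of 16 patients (Section 3.2).

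**Formula.** After x failures in n patients the posterior is Beta(2+x, 6+n−x). With integer parameters its tail is an exact binomial sum:

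P(rate > 0.25 | x of n) = P(Y ≤ 1+x), where Y ~ Binomial(7+n, 0.25).

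**Step 1: the plan's own prior figure.** The prior mean is 2/(2+6) = 0.25, as stated. With n = 0 and x = 0, P(Y ≤ 1) for Binomial(7, 0.25) is 0.75⁷ + 7 × 0.25 × 0.75⁶ = 0.1335 + 0.3115 = 0.4449. This agrees with the stated 45% to within rounding, so the model is being read as intended.

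**Step 2: the boundaries.** For each n from 2 to 16, take the smallest x with posterior at least 0.70. The values around each change-over are:

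| n | Posterior with one failure fewer than Table 1 requires | Posterior at the Table 1 count | Table 1 | Rule |
|---|---|---|---|---|
| 4 | 1/4: 0.4552 | 2/4: 0.7133 | 2 | 2 |
| 5 | 2/5: 0.6488 | 3/5: 0.8424 | 3 | 3 |
| 7 | 2/7: 0.5213 | 3/7: 0.7415 | 3 | 3 |
| 8 | 3/8: 0.6865 | 4/8: 0.8516 | 4 | 4 |
| 10 | 3/10: 0.5739 | 4/10: 0.7653 | 4 | 4 |
| **11** | **4/11: 0.7175** | 5/11: 0.8610 | **5** | **4** |
| 12 | 4/12: 0.6678 | 5/12: 0.8251 | 5 | 5 |
| 13 | 4/13: 0.6172 | 5/13: 0.7858 | 5 | 5 |
| **14** | **5/14: 0.7436** | 6/14: 0.8701 | **6** | **5** |
| 15 | 5/15: 0.6994 | 6/15: 0.8385 | 6 | 6 |
| 16 | 5/16: 0.6537 | 6/16: 0.8037 | 6 | 6 |

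The sample sizes not shown (2, 3, 6 and 9) also agree. For the two mismatches, 4/11 is P(Y ≤ 5) for Binomial(18, 0.25) = 0.7175, and 5/14 is P(Y ≤ 6) for Binomial(21, 0.25) = 0.7436.

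The ranges that follow from the rule are therefore 2-4, 5-7, 8-11, 12-14 and 15-16. Table 1 matches at 13 of 15 sample sizes and is one failure too high at the other two.

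**Step 3: could a different reading rescue the table?**
- Rounding to two decimals gives 0.72 and 0.74, both still above 0.70.
- A strict inequality changes nothing, since both values exceed 0.70.
- Another cutoff with the same prior fails. Continuing at 5/14 requires a cutoff above 0.7436, and stopping at 2/4 requires one of at most 0.7133.
- Some other priors do give the table. A flat Beta(1,1), for example, does so with a cutoff above 0.8516 and up to 0.8854. That is not the rule in Section 5.4.

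**Step 4: can the two cells be reached?** Yes. Table 1 continues at 3/10 and at 4/13, so a failure in patient 11 leads to 4/11 and a failure in patient 14 leads to 5/14.

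**Step 5: operating characteristics.** These come from an exact forward recursion with a look after every patient from the second, assuming all 16 patients are in one stratum:

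| True failure rate | P(stop), Table 1 | P(stop), stated rule | Difference (points) |
|---|---|---|---|
| 25% | 41.6% | 44.3% | 2.7 |
| 40% | 81.3% | 83.4% | 2.1 |
| 50% | 94.7% | 95.5% | 0.8 |

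**The case against.** The arithmetic is not in dispute; the case on the other side is about importance.

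- **Allocation.** The rule runs within each stratum and only 16 patients are planned, so at most one stratum can reach 11. With splits from 8/8 to 10/6 the table and the rule coincide at every reachable count. At a stratum size of 10, both stop with probability 37.2% at a true rate of 25% and 72.9% at 40%. The figures for one stratum of 16 describe an extreme allocation. This stands, although no split is fixed, and a stratum that ends at exactly 11 or 14 would show a gap of 3.5 to 4.8 points at true rates of 25% to 40%.
- **Rarity and short duration.** Under Table 1, 4/11 is reached only if the fourth failure is patient 11, with probability 3.5% at a true rate of 25% and 4.8% at 40%. For 5/14 the figures are 2.4% and 3.4%. If the next patient completes, the rule itself no longer calls for stopping (4/12 = 0.6678, 5/15 = 0.6994). This also stands.
- **Discretion.** The text speaks of considering a stop, so crossing 0.70 prompts a judgement. That softens what follows a trigger, not when it is met, and Table 1 itself says to stop.
- **Which governs.** Nothing says the table overrides the text. That is true, but nothing says the reverse either, so the conflict stays open.
- **Other safeguards.** Appendix 2 provides monthly review of each participant's results and DSMC review of serious events. These limit harm but do not correct the boundary.
- **What is counted.** Section 5.4 applies the prior to high-grade toxicity, while Table 1 counts shortfalls in cisplatin dose. This separate inconsistency also needs resolving; it does not alter the Beta calculation.

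**Conclusion.** The concern holds. Under the prior and cutoff in Section 5.4, Table 1 is wrong at 11 and 14 patients, each time by one failure and each time in the permissive direction. No choice of cutoff with the stated prior makes it right. The conclusion rests only on figures in the protocol.

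The practical effect is small: 2 to 3 points in the probability of stopping at true rates of 25% to 40%, assuming all 16 patients are in one stratum and are monitored after every patient from the second. It is zero if neither stratum reaches 11. No primary estimate or sample-size statement depends on it. The reason to correct it is that a stopping boundary contradicts its own definition, not that the trial's behaviour would change much.

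**What to change.** Replace the patient ranges in Table 1 with those that follow from the rule:

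| Failures needed to stop | 2 | 3 | 4 | 5 | 6 |
|---|---|---|---|---|---|
| Patients | 2-4 | 5-7 | 8-11 | 12-14 | 15-16 |

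If the printed table is the one the investigators want, Section 5.4 should instead give the prior and cutoff that produced it; Beta(2,6) cannot be kept in that case. Either way, add a sentence saying whether the table or the posterior probability governs.

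The cost is an edit to one table row, or to the rule's parameters, by protocol amendment. It needs no extra patients, visits or data.
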